7.3.2 Computer Assisted Self-Interview

Demographic, social, behavioral, and attitudinal measures will be collected using CASI developed within Qualtrics. The CASI responses will remain confidential; no personal identifying information will be collected. Detailed instructions regarding completion of the CASIs will be provided in site MOPs.

7.3.2.1 CASI Data Security

The CASI data will be collected on iPad devices using Qualtrics. Qualtrics is a web-based system appropriate for use with sensitive data, including those data protected by the Health Insurance Portability and Accountability Act of 1996 (HIPAA). Data are stored on secure servers and protected by fire walls. No data is written to the iPad hard drive.

7.3.3 Audio Data for UBACC and Debriefing Interviews

The entire study visit, including UBACCs and debriefing interviews, will be digitally audio-recorded with participant consent. Immediately upon completion, the digital audio files will be uploaded to the Indiana University (IU) secure server. The audio recordings will be uploaded to a secure website belonging to a transcription company, who will listen to the recordings, transcribe them into a Microsoft Word file, and upload the transcript files to their secure website for download by IU study staff. Transcripts will be checked against audio recordings for accuracy. Once that process is complete, the audio files will be destroyed. [name] will ensure that the audio files are destroyed by the transcription company, and permanently deleted from the IU server.

7.3.4 Electronic Case Report Forms

Data regarding study completion/early termination and protocol deviations will be collected using eCRFs developed within Qualtrics. The eCRFs will remain confidential; no personal identifying information will be collected. eCRFs will have the participants ATN Study ID number associated with the answers. Detailed completion guidelines for the eCRFs will be provided in the MOP.

7.4 Data Submission

All CASI and CRF data will be collected in electronic format using Qualtrics. For both the UBACC administration and debriefing interview data, the digital audio files will be uploaded to the IU

secure server. Then IU study staff will upload the digital audio files to a secure website belonging to a transcription company, who will listen to the recordings, transcribe them into a Microsoft Word file, and upload the transcript files to their secure website for download by IU study staff.

All data will be submitted to the NICHD's Data and Specimen Hub (DASH) after completion of the study in accordance with the NICHD DASH Data Archive Policy (<https://dash.nichd.nih.gov/Resource/Policies>) and the NIH Grants Policy Statement (<https://grants.nih.gov/grants/policy/nihgps/HTML5/introduction.htm>).

7.5 Data Quality Assurance

Investigators receiving federal funding must adhere to the Code of Federal Regulations (CFR) to protect research participants and produce reliable study information. Sites participating in research sponsored by the NICHD need to have an internal quality assurance (QA) plan that will identify problems and correct errors in research study records.

For debriefing interviews, data quality will be checked at two time points. Two team members will listen to segments of each debriefing interview digital recording for recording quality and completeness and each transcription will be checked against the debriefing interview digital recording for accuracy and completeness.

7.6 Role of Data Management

Indiana University is responsible for all eCRFs and CASI administration as well as data collection and cleaning. The IU Data Manager will assist in protocol development and data analysis. The IU Data Manager will regularly receive data transfers from the Qualtrics database system for the purposes of producing study monitoring reports and/or to perform data analyses described in the statistical analysis plan or approved publication requests. Any data issues discovered by the DM will be reported to the PI and corrected in the Qualtrics database.

7.7 Study Site Monitoring and Record Availability

Site monitors from the CC will visit participating study sites to review compliance with the protocol, as well as accuracy and completeness of relevant study documentation and records, such as training logs. Regulatory files, as required, will also be inspected to ensure that regulatory requirements are being followed. Each site will work with the monitors to arrange a monitoring visit to ensure appropriate RS are available and that all documentation is accessible. Internet access will be required as well as appropriate space for the monitor to work.

Activities that may be performed and documents that may be reviewed by the monitor include review of study procedure and documentation regarding compliance with protocol, GCP, and regulatory requirements.

At the end of the monitoring visit, the monitor will meet with the PI, the study coordinator, and any other relevant RS to go over the findings.

7.8 Study Monitoring

Implementation of the study will be monitored by the Study Team Review Committee (STRC), which includes the Protocol Chair, NICHD Health Science Administrator, one co-Investigator, Consent 2.0 Program Manager, and the IU Data Manager.

7.8.1 Monitoring by Study Team Review Committee (STRC)

The STRC will meet at least monthly. During these meetings, the STRC will review enrollment reports, reports on early discontinuation of the one-day study visit, and reports on Untoward Events (UEs) that have occurred since the last STRC meeting or previously reported UEs for which new information is available. All UEs will be reviewed within one week of occurrence; if the next scheduled STRC meeting is more than 7 days after a UE occurred, the team will convene a special meeting to address it.

In the event that an UE occurs at a research site, the STRC will invite the relevant Site PI to attend either the regular STRC meeting or a specially convened meeting (see next section). During the STRC meeting the UE will be reviewed and the team will determine what actions are necessary. The Site PIs for Consent 2.0 will not be standing members of the STRC.

8.0 PARTICIPANT MANAGEMENT

8.1 Study Visit Management

This project requires one study visit. There are no follow up visits.

If an eligible participant does not show for a scheduled study visit, the RS will follow up and make at least three attempts to reschedule. Similarly, RS will make at least three attempts to contact all participants who are eligible and interested but unable to complete the study visit on the same day as screening questionnaire. Participants will be considered off study due to loss to follow up if they fail to respond or attend the study visit after the three attempts at contact/rescheduling.

8.2 Compensation

All participants will receive \$50, in cash or gift card to compensate for their time. An additional \$25 will be provided to participants who complete the debriefing interview. Each site will determine the most appropriate form of compensation. Gift cards may be: a Visa card, gas card, card for specific local store [e.g. Target, Wal-Mart]. In addition, sites may offer reimbursement for transportation. Each site will determine the most appropriate form of transportation reimbursement (e.g. bus fare, subway tokens, taxi vouchers, or cash). Participants who make a separate or unnecessary trip to the study site for screening but are deemed ineligible for any reason—including lack of interest—will receive \$10 (cash or gift cards) as well as \$5 transportation reimbursement (e.g. bus pass). These incentives will be available to any participant who screen fails until online screening has been established. After online screening has been established, RS may provide these incentives on a case by case basis at their discretion (e.g. in case someone cannot screen online and needs to come to the study site to

screen) Participants will receive \$50 if they only stayed for part of the study visit. Participants will not receive any compensation for completing the online screening questionnaire.

8.3 Intervening on “Social Harms”

All sites have specific policies governing the treatment of human subjects. These policies specify that medical and psychological assistance will be available in the immediate environment in the event a participant should experience any adverse reactions resulting from study procedures.

While participants will be informed that they may refuse to answer any question at any time, responses or reactions to certain questions may indicate distress on the part of the participants. If at any time during the study, a participant divulges that he or she is at risk for harm, including but not limited to being abused or experiencing violence, if harm is suspected or likely, or if the participant states he or she is suicidal/homicidal, measures will be taken to ensure his or her safety. Reporting will be done as appropriate to the situation and the legal statutes, including reporting to child protection agencies or other appropriate agencies and referrals will be provided to appropriate support, counseling or treatment resources.

8.4 Criteria for Premature Discontinuation

Study participants will only complete one study visit. No participant follow up will be conducted; therefore premature study discontinuation will be limited to the following reasons:

8.4.1 Consent or assent withdrawn during CASI or interview;

8.4.2 Development of an untoward effect that warrants discontinuation from study; or

8.4.3 Failure to adhere to or complete study evaluations;

If it becomes apparent that a participant is becoming increasingly distressed while participating in any part of the study, the individual will be assessed by the RS (or designee) to determine whether they will be able to complete the session without experiencing undue distress. If the participant appears unable or refuses to continue participation, they will be offered a list of referral sources.

9.0 MONITORING UNTOWARD EFFECTS ASSOCIATED WITH OR RESULTING FROM STUDY

RS must follow the sIRB's procedure for reporting and managing untoward events (UEs). ATN protocols follow the ATN Manual of Policies and Procedures (MOPP) for UE reporting. The ATN Query Notification System (QNS) will be used to document the occurrence of an UE, as well as to provide the details, grading and rating of related or unrelatedness to the study. Protocol team members are notified through the ATN QNS.

9.1 Untoward Events Reporting

RS will enter any UE of grade 3 or above in the ATN QNS (<https://www2.cscc.unc.edu/atn/node/add/untoward-event-150>) within 48 hours of site awareness. Other events (Grades 1 and 2) will be expected to be entered in the ATN QNS within 7 days of site awareness of the untoward event.

All reported events will receive a grade by the RS. The grades are defined as noted below. The functional table below should be used to grade the severity of an UE. In addition, all deaths related to the study are to be classified as **grade 5**.

Table 3: Untoward events grading

PARAMETER	GRADE 1	GRADE 2	GRADE 3	GRADE 4	GRADE 5
	MILD	MODERATE	SEVERE	POTENTIALLY LIFE-THREATENING	DEATH
Event NOT identified elsewhere in the grading table	Mild symptoms causing no or minimal interference with usual social & functional activities with intervention not indicated	Moderate symptoms causing greater than minimal interference with usual social & functional activities with intervention indicated	Severe symptoms causing inability to perform usual social & functional activities with intervention or hospitalization indicated	Potentially life-threatening symptoms causing inability to perform basic self-care functions with intervention indicated to prevent permanent impairment, persistent disability, or death	Death
Examples	Discomfort over survey questions that were self-resolved or resolved without team intervention	Mild to moderate distress observed by study team resolved with team intervention.	Severe emotional distress observed by study team requiring evaluation or intervention.	Suicidal ideation or suicide attempt while on study.	Death

Adapted from <https://rsc.tech-res.com/docs/default-source/safety/daids-ae-grading-table-mar2017.pdf?sfvrsn=6>

The Study Team Review Committee (STRC), listed above in Section 7.8, are responsible for systematically reviewing all new UEs on regularly scheduled conference calls.

The Coordinating Center (CC) is responsible for presenting a cumulative report of all UEs reported in the ATN QNS for ATN 150. All UEs will be reviewed within one week of occurrence;

if the next scheduled STRC meeting is more than 7 days after a UE occurred, the team will convene a special meeting to address it.

When an UE occurs at a research site, the STRC will invite the relevant Site PI to attend either the regular STRC meeting or a specially convened meeting. During the STRC meeting the UE will be reviewed and the team will determine what actions are necessary. The Site PIs for Consent 2.0 will not be standing members of the STRC.

The CC will follow required reporting procedures and related timelines. RS must also follow the sIRB's procedure for reporting these untoward events. For any events where it is learned that community members or RS members experience negative events associated with the study, the event will be reported to the STRC for review and determination of outcomes.

9.2 Reportable Events by Populations

There are three types of untoward events to be identified: (1) those related to the participating adolescent or parent, (2) those related to the RS, (3) those related to the community.

First, the study will catalogue any untoward event experienced by the participant that may be attributable to participation in or the conduct of the study. Reporting is required for occurrences including social harms and psychological distress, and serious life-threatening events such as suicide attempts. These may be immediately apparent to the RS, such as the participant's emotional upset requiring referral for counseling; or they may be delayed and reported later to R, such as physical harm to a participant for having participated in the study.

Second, RS may encounter untoward events during the conduct of this study that personally affect them. Training and guidance will seek to minimize this risk. Nonetheless, an assessment of the cost of conducting this study must include cataloguing these events as well. The Protocol Team should be notified of these events using the ATN QNS so that they may be immediately addressed, evaluated, and guidance modified or expanded to minimize similar risk to other staff.

Third, the community may also be affected by an UE. Examples of community level UEs include any adverse community feedback received by the research institution or team concerning the study and the study being portrayed adversely in any community forum or in the media. RS will also report any UEs that affect the community in the ATN QNS. Both staff and community level untoward events do not receive a grade.

10.0 STATISTICAL AND ANALYTIC CONSIDERATIONS

10.1 Study Design

This study will use a quasi-experimental design to explore how the informed consent process affects the acceptability of biomedical HIV prevention trials, from the perspective of behaviorally high-risk minor adolescents and the parents of minor adolescents.

Adolescent participants will undergo a simulated consent process for each of two hypothetical studies based on their randomized consent condition. Hypothetical Study 1, modeled after ATN 113, is an open-label study of oral TDF-FTC and hypothetical Study 2, modeled after HPTN 077,

is a Phase IIa trial of an injectable HIV integrase inhibitor. After completing the simulated consent process for the first hypothetical study, the adolescent will complete a CASI assessing the adolescents' WTP and will work with RS to complete the UCSD Brief Assessment of Capacity to Consent (UBACC).²⁸ The simulated consent process and follow-up assessments will then be completed for the second hypothetical study. The presentation order for the two hypothetical studies will be randomly determined (see Section 3.3 for more details on the randomization procedure).

Parent participants will review all three consent conditions for each of the two hypothetical studies and complete a CASI assessing the acceptability of the three approaches to consent. The presentation order of the hypothetical studies and the review order for the consent conditions for each hypothetical study will be randomly determined (see Section 3.3. for more details on the randomization procedure).

10.2 Study Endpoints

There are primary key endpoints for this study:

1. Adolescent WTP scores (values 1 through 5) converted from a Likert scale (definitely not participate, probably not participate, might or might not participate, probably participate, definitely participate). Adolescent WTP scores are the measured adolescent response to the question: "If offered the chance, how likely would you be to participate in the first/second study?"
2. Parental WTS scores are the measured parent response to three vignettes. Parents are asked the same vignettes after listening to Study 1 and Study 2. The vignettes and study orders are varied.
 - a. Vignette 1 states: "Imagine your teen wants to join the study we just described. Your teen asks you to come to the research clinic with them. You are given information about the study, and have the opportunity to ask any questions you want to ask. After your questions are answered, you are asked to give your permission for your teen to join the study. In this approach to consent, you have the final say about whether your teen can join the study. How acceptable is this approach to research consent?"
 - b. Vignette 2 states: "Imagine your teen wants to join the study we just described. Your teen comes to the research clinic on their own. They read the consent form, and have an opportunity to ask questions. Your teen is required to have an adult's permission to sign up for the study. They can choose to ask either you or a neutral adult, called an "ombudsman." The ombudsman is not in charge of the study; the ombudsman's job is to ensure your teen understands the research study, and to help your teen think about the risks and benefits of joining the study. Your teen would need either your permission OR the ombudsman's permission to join the study. In this approach to consent, your teen must have an adult's permission to join the study; your teen would be able to choose whether to seek permission from you or the ombudsman. How acceptable is this approach to research consent?"

c. Vignette 3 states: "Imagine your teen wants to join the study we just described. Your teen comes to the research clinic on their own. They read the consent form, and have an opportunity to ask questions. Once their questions are answered, your teen is ready to consent to the study. They are allowed to sign the consent form without speaking to anyone else about the decision. In this approach to consent, your teen is allowed to make the decision about joining the research study on their own. How acceptable is this approach to research consent?"

The vignette responses are based on a 5-point Likert scale with values ranging from 'completely unacceptable' to 'completely acceptable.'

Of note, more comprehensive data are collected regarding parental WTS for the three consent conditions, including: (1) measures of the parent's perception of his/her adolescent's capacity to consent to the two studies in question and (2) a measure of the parent's expectation that his/her teen would discuss the study prior to enrollment, even if such a discussion were not required. Since these measures are not applicable to all consent conditions, they were not used in the definition of the primary endpoint.

10.3 Sample Size and Power Estimates

This study is powered to detect a meaningful difference in adolescent WTP scores and to detect a meaningful difference in parental WTS scores between the three consent conditions being studied. The WTP scores will be estimated as the mean score of three 5-point Likert scales. Based on the assumption that adolescent WTP scores are normally distributed and analyses using a linear regression model based on 120 participants (40 per consent condition) and with 7 independent variables in the model will provide 80% power to detect a $0.09 f^2$ effect size, which is between a small ($f^2=0.02$) and a medium effect size ($f^2=0.15$), for consent conditions. This power calculation, which assumed a single observation per participant, is conservative and the actual study which will have two observations per participant (one for each simulated consent process) will have a larger statistical power to detect an $f^2=0.09$ effect size for consent condition. Since the test of consent condition effects based on parental WTS scores is a within-participant comparison rather than an across-participant comparison, a test of parental consent condition effects will have 80% power to detect an even smaller effect size (f^2) compared to tests for consent condition effects using adolescent WTP scores.

A subset of 24–32 (6–8 per study site) adolescents and 24–32 (6–8 per study site) parent participants will be selected to participate in the debriefing interview. Prior research with similar populations suggest that this sample size is sufficient for eliciting a variety of perspectives and establishing key themes in the data.

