3.2 Sample Size

This study will enroll approximately 144 (36 per study site) high-risk minor adolescents and 144 (36 per study site) parents of adolescents. A subset of 24-32 (6-8 per study site) adolescents and 24-32 (6-8 per study site) parents will be selected to participate in the debriefing interview. Of note, the adolescents and parents will not be parent-child dyads; they will be unrelated. We project total enrollment of 288 participants, however, since this is a multi-site project with simultaneous recruitment with a hard to reach population, we may schedule and enroll more subjects than anticipated.

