4.3 Recruitment and Screening

This study will recruit adolescents between ages 14-17, inclusive, and parents of adolescents in the same age range. Participants will be recruited from four partnering research sites in the following U.S. cities: Baltimore, MD (partnering organization: Johns Hopkins University, partnering researcher: [name]), Chicago, IL, (partnering organization: University of Chicago, partnering researcher: [name]), Denver, CO (partnering organization University of Colorado, partnering researcher: [name]), and Tampa, FL (partnering organization University of South Florida, partnering researcher: [name]).

Specific recruitment procedures for each group are described in detail below.

4.3.1 Adolescents aged 14-17:

This study will recruit 36 adolescents at each site primarily through contact in the clinical setting. If recruitment is slow, we will begin using advertising on social media (Facebook, Twitter, chat services); support centers for lesbian, gay, bisexual, transgender, and questioning (LGBTQ) youth; churches and other social settings (e.g. Gay Straight Alliance at local high schools) and at clinics affiliated with the partnering organization. All interested adolescents will complete a screening questionnaire that should take about 10 minutes to complete.

Adolescents recruited in person will complete the questionnaire on a tablet on the same day they are recruited. Adolescents who self-refer or hear about the study from friends will need to complete the screening questionnaire online. All eligible adolescents will provide contact information regardless of recruitment and screening method.

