10.4 Statistical Analysis Plan

10.4.1 Quantitative Data Analysis

The primary analyses will estimate the effect of the three conditions and two hypothetical trial types on adolescent WTP scores and parent WTS scores. All analyses will be performed separately for adolescents and parents. The type I error rate will be set to $\alpha = 0.05$ separately for adolescent-specific and parent-specific hypothesis tests.

Linear mixed models will be used to estimate the effect of the three consent conditions and two trial types on WTP and WTS scores, with a random participant effect (i.e. random intercept) to account for the potential correlation between the multiple responses per participant. Aside from consent condition and trial type effects, the LMMs will also include adolescent's sex assigned at birth and study site as fixed effects.

Heterogeneity of consent condition and trial type effects across study sites will be evaluated. If statistically significant interactions occur ($p<0.05$), site-specific estimates of effects will be presented to supplement the pre-planned analyses. P-values from pairwise comparisons of consent condition effects will be adjusted for multiple comparisons to control the type I error rate at the level $\alpha=0.05$ separately for parents and adolescents. Tests of trial type effects will be performed at the level $\alpha=0.05$ separately for adolescents and parents and separately from tests of consent condition effects.

As a secondary sensitivity analysis, we will evaluate whether concern about HIV, family context (frequency of communication, connectedness), and other demographic and socioeconomic factors affect WTP/WTS participation in biomedical research. We will examine these effects by adding variables into the models to determine if they moderate the relationship between consent condition and WTP/WTS scores.

Although WTS and WTP scores are discrete, it is common to analyze these data using linear models. Research suggests that this approach is robust to the discrete nature of the data if the normality assumption is not severely violated. However, usage of the LMM may be problematic if a large number of responses occur on the boundary (e.g. a high proportion of 1's or 5's). In this case we will fit a linear quantile mixed model for the median WTP and WTS scores, which does not require normality.³⁴

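### Section 10.3 computes adolescent power for 120 participants, but the plan enrols about 144; the sections disagree and the power is understated, not short

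*Combined protocol and SAP*

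**What the plan says.** Section 10.3 bases the adolescent calculation on a "linear regression model based on 120 participants (40 per consent condition"), "with 7 independent variables in the model", and reports "80% power to detect a $0.09 f^2$ effect size" for consent condition. It adds: "This power calculation, which assumed a single observation per participant, is conservative". The reason offered is the second WTP score per adolescent; the number of participants is not mentioned. Section 10.3 states neither alpha nor the numerator degrees of freedom. Section 10.4.1 supplies alpha: "The type I error rate will be set to $\alpha = 0.05", separately for adolescents and parents.

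The design sections use a different number. Section 3.2: "This study will enroll approximately 144 (36 per study site) high-risk minor adolescents". Section 4.3.1: "This study will recruit 36 adolescents at each site". The abstract agrees. Sections 3.3 and 5.2.1 randomise adolescents 1:1:1 to three consent conditions.

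**The concern.** The only quantitative justification for the adolescent sample size is calculated for a number that the plan does not intend to enrol. Forty per condition appears nowhere in the design sections; 144 / 3 gives 48.

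Nothing in the text connects the two figures. There is no dropout or non-evaluable allowance, and 120 is not called a minimum. The study is one visit without follow-up (section 8.1), participants start procedures straight after verbal consent (section 5.1), and section 3.2 allows for enrolling more than planned.

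Two things are at stake. A reader would take 80% power at f² = 0.09 as the design sensitivity of the Aim 1 primary test, when the planned number gives more. And section 10.3 as written justifies 120 adolescents and leaves the other 24 unexplained. The parent power sentence is affected too, because it is stated only relative to the adolescent figure.

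**Working it through.** **Inputs**
- N = 120 (40 per condition), from section 10.3; N = 36 × 4 = 144 (144 / 3 = 48 per condition), from sections 3.2, 4.3.1 and 3.3.
- 7 independent variables, from section 10.3. This fits the model in 10.4.1: consent condition 2 + trial type 1 + sex 1 + site 3 = 7.
- Numerator df u = 2. Inferred from three conditions; not stated.
- Alpha = 0.05, from section 10.4.1.
- One observation per participant, as section 10.3 assumes.

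**Formula.** Power = P(F′ > F crit), where F′ is noncentral F with u = 2 and v = N − 7 − 1 df. Section 10.3 does not say which noncentrality λ it used, so three standard choices were tried: f²·v, f²·(u + v + 1) and f²·N.

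**N = 120, to reproduce the plan's figure** (v = 112, F crit = 3.077)

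| λ | λ at f² = 0.09 | Power at f² = 0.09 | f² for 80% power |
|---|---|---|---|
| f²·v | 0.09 × 112 = 10.08 | 80.8% | 0.0884 |
| f²·(u+v+1) | 0.09 × 115 = 10.35 | 81.9% | 0.0861 |
| f²·N | 0.09 × 120 = 10.80 | 83.5% | 0.0825 |

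The first two rows round to the stated 0.09 and lie within 2 points of 80%. The calculation in section 10.3 is therefore sound for 120 participants.

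**N = 144, the planned number** (v = 136, F crit = 3.063)

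| λ | λ at f² = 0.09 | Power at f² = 0.09 | f² for 80% power |
|---|---|---|---|
| f²·v | 0.09 × 136 = 12.24 | 88.2% | 0.0724 |
| f²·(u+v+1) | 0.09 × 139 = 12.51 | 88.9% | 0.0709 |
| f²·N | 0.09 × 144 = 12.96 | 90.1% | 0.0684 |

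Reaching 80% at f² = 0.09 takes only 119, 116 or 111 participants under the three choices. None of them makes the stated pair belong to 144.

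**In SD units.** With equally spaced condition means −d/2, 0 and d/2 and equal groups, f² = d²/6, so the gap between the extreme conditions is d = √(6f²) residual SDs. At 80% power in both cases:
- N = 120: √(6 × 0.0825) = 0.70 to √(6 × 0.0884) = 0.73 SD.
- N = 144: √(6 × 0.0684) = 0.64 to √(6 × 0.0724) = 0.66 SD.

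**Second observation.** With two scores per adolescent and within-person correlation ρ, the noncentrality for a between-participant effect is multiplied by 2/(1 + ρ), so the detectable f² is multiplied by (1 + ρ)/2. The documents give no ρ, so a range is assumed. At N = 144:
- ρ = 0.1: 0.55 × (0.0684 to 0.0724) = 0.038 to 0.040.
- ρ = 0.5: 0.75 × (0.0684 to 0.0724) = 0.051 to 0.054.
- ρ = 0.9: 0.95 × (0.0684 to 0.0724) = 0.065 to 0.069.

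**Parent quotas.** 15 + 15 = 30 per site × 4 = 120 (abstract and section 3.3); 18 + 18 = 36 per site × 4 = 144 (section 5.2.2).

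**The case against.** The strongest reply is that nothing is lost. A trial planned with 144 adolescents has at least the power claimed for 120, and section 10.3 already tells the reader that its figure is conservative. The arithmetic in 10.3 is right on its own terms. A completed trial will in any case be read from its estimates and intervals, not from a planning figure. And the one-observation simplification, which section 10.3 discloses, can move the detectable f² as much as the difference between 120 and 144 does.

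Most of this stands. It limits the point to an inconsistency between sections and makes it modest in weight. It does not remove it: the conservatism that 10.3 discloses comes from ignoring the second score, and says nothing about using a smaller sample than planned.

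The 120 could also be meant as an evaluable number: 120 / 144 = 83.3%, a loss of 16.7%. That is possible, but no section says so, and a single visit makes a loss of that size something to state. The parent quotas suggest another explanation, a leftover target of 30 per site, but that is inference.

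From the mismatch a reader might infer that the trial is underpowered, or that the stated 80% at f² = 0.09 is false for it. The documents support neither reading: the planned number is larger than the one used in the calculation, and the claim holds with room to spare.

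**Conclusion.** The inconsistency is real. The pair of 80% power and f² = 0.09 belongs to 120 participants; the plan enrols about 144. The effect is to understate power, and the stated pair remains true as a lower bound. With one observation per participant, the planned sample gives 88-90% power at f² = 0.09 where 120 gives 81-84%, and the f² detectable with 80% power falls from 0.082-0.088 to 0.068-0.072. For equally spaced conditions, the extreme gap falls from about 0.70-0.73 to 0.64-0.66 SD. Counting the second observation lowers the detectable f² at 144 to about 0.04-0.07 for within-person correlations of 0.1 to 0.9.

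These figures rest on a 2-df test (inferred), alpha 0.05 taken from section 10.4.1, full enrolment of 144 and, for the last range, assumed correlations.

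**What to change.** Restate section 10.3 for 144 adolescents, 48 per condition: 80% power for f² of about 0.07, or about 88-90% power at f² = 0.09, with one observation per participant. State alpha and the numerator df there so that the figure can be reproduced. If 120 is meant as a minimum evaluable number, say so, give the assumed loss, and report both figures.

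At the same time, reconcile the parent quotas: 15+15 per site in the abstract and section 3.3 against 18+18 in section 5.2.2, where section 3.2 plans 144 parents.

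The cost is a few sentences. Enrolment and analysis do not change.
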